Redfield et al, 2013 ¹⁰ double-blind, randomized, placebo- controlled	HFpEF	216 (113 sildenafil)	None	20 mg TIDx 12 weeks, followed by 60 mg TID for 12 weeks.	6 months	No improvement in exercise capacity or clinical status
Amin et al, 2013 ²⁰ double-blind, randomized, placebo- controlled	NYHA II/III EF<35%	106	None	25-50 mg TID	12 weeks	No improvement in exercise capacity or clinical status

1. Specific hypotheses

Phosphodiesterase- 5 inhibitors in heart failure with secondary reactive pulmonary hypertension improve exercise capacity, hemodynamic, echocardiographic parameters, and quality of life

2. Trial design

Patients over 18 years of age with HF who have PH by right heart catheterization (mean pulmonary artery pressure \geq 25 mm Hg, pulmonary capillary wedge pressure \geq 15 mm Hg, and pulmonary vascular resistance $>$ 3WU) will be eligible for randomization to sildenafil 20 mg, or placebo three times a day for 3 months. At baseline, a 6 minute walk test and quality of life questionnaire will be performed (Kansas City Cardiomyopathy Questionnaire) from 7 days prior to 3 days after qualifying right heart catheterization. If the echo was done for clinical indications within one month of enrollment, the data will be used. Laboratory tests are routinely obtained before right heart catheterization (comprehensive metabolic panel and NT-proBNP) and will be recorded for the study.

Participants will return for follow-up visits as needed for clinical indications. Our study coordinator will document changes of symptoms, changes in therapies, and capture clinical events like unscheduled hospital visits. For study purpose, the only follow-up visit will take place in 3 months. At that time, an echocardiogram, right heart catheterization, six minute walk, laboratory tests, and quality of life questionnaire will be repeated if clinically indicated. In addition, we will evaluate for signs and symptoms of HF (dyspnea, increased cough, paroxysmal nocturnal dyspnea, peripheral edema, S3 gallop, increased heart rate) at baseline and at the follow-up visit. These assessments are part of routine care for HF patients. The 3 month assessments should take place from 80-97 days following randomization whenever possible.

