Measurements and calculations by 2D echo will include left ventricular end systolic and end-diastolic dimensions, left ventricular ejection fraction by Simpson's method, left atrial volume, severity of mitral and tricuspid regurgitation, velocity of tricuspid regurgitation, diameter of inferior vena cava and its variability with respirations, and right ventricular function by tricuspid annular plane systolic excursion.

Measurements by right heart catheterization will include right atrial pressure, right ventricular systolic and end diastolic pressure, pulmonary arterial systolic, diastolic, and mean pressure, and pulmonary capillary wedge pressure. Cardiac output and cardiac index will be calculated both by Fick and thermodilution methods.

The majority of study information will be collected from routine care for standard clinical indications.

Primary outcome

6 minute walk distance

Secondary outcomes

Percent of change of pulmonary arterial pressures (systolic, diastolic, and mean) and pulmonary vascular resistance from the baseline

Percent of change of cardiac index from the baseline

Percent of change in tricuspid annular plane systolic excursion

3. Objectives

Primary Objective:

The primary objective of this study is to determine whether sildenafil for treatment of HF with reactive PH can improve exercise tolerance measured by 6 minute walk distance

Secondary Objectives:

The secondary objectives of this study are to determine whether sildenafil for treatment of HF with reactive PH can improve hemodynamics, right ventricular function, or quality of life

4. Eligibility (include rationales for selecting or excluding particular cohorts)

Inclusion criteria:

[figure not shown]
- ≥ 18 years of age
- Known chronic heart failure appropriately treated with angiotensin converting enzyme antagonists, angiotensin receptor blockers, and beta blockers, unless contraindicated, not indicated, or poorly tolerated
- Indications for right heart catheterization, other than for biopsy
- Pulmonary artery mean pressure >25 mm Hg, pulmonary capillary wedge pressure >15 mmHg, and pulmonary vascular resistance >3 WU as measured by right heart catheterization within 3 days of planned randomization

Exclusion criteria:

- Hypersensitivity, allergy, or intolerable side effects of sildenafil

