- Contraindication to sildenafil including need for nitric oxide donors such as organic nitrates or organic nitrates in any other form regularly and/or intermittently or current nitrate therapy
- History of primary PH, connective tissue disorders, severe COPD, pulmonary embolism, or left to right shunts
 - Primary (idiopathic) Pulmonary Hypertension in patients without history of heart failure
 - Pulmonary hypertension in patients with systemic scleroderma
 - Pulmonary hypertension due to congenital heart disease
 - Pulmonary hypertension due to severe COPD
 - Pulmonary hypertension in patients with systemic scleroderma
 - Pulmonary hypertension due to congenital heart disease
 - Pulmonary hypertension due to severe COPD or interstitial lung disease
- History of heart transplant, VAD, or any other solid organ transplant
- Likely to have solid organ transplant or any other major surgery during study enrollment/treatment period
- Liver cirrhosis as primary diagnosis

- History of massive pulmonary embolism
- Acute pulmonary embolism
- Female subject who is pregnant, breastfeeding, or one who is unwilling to practice an acceptable method of birth control unless postmenopausal or sterile.
- Unreliability as a study participant based on the investigator's (or designee's) knowledge of the subject (eg, alcohol or other substance abuse, inability, unwillingness to adhere to the protocol, documented non-compliance or vulnerable population
- Currently enrolled in another investigational drug or device clinical study, or less than 30 days since completing study
- Current diagnosis of HIV or AIDS
- End stage renal disease undergoing dialysis
- End stage liver disease
- Co-morbidities, if it limits exercise tolerance
 - morbid obesity (BMI>40)
 - COPD with oxygen dependence
 - severe peripheral vascular disease with intermittent claudication
 - status post amputation of lower extremity(s) at any level
 - severe degenerative joint disease preventing normal walking
 - CVA with long term sequella affecting ability to walk

5. Arms/regimens

6. Statistical design in detail (include one primary and any secondary endpoint(s), any stratification to be used in the randomization, sample size with power justification, analysis plan including plans for formal interim analysis, projected monthly accrual rate)

Sample size was calculated at 32 patients per arm, 64 patients total

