Primary and secondary endpoints are as noted above. Patients will be randomized to treatment versus placebo in a 1:1 ratio using permuted blocks of variable size, to which the principal investigator (and the patients themselves) will be blinded. Planned sample size is 64, as described below. Data will be analyzed on an intent-to-treat basis, as described below. An interim analysis will also take place after data have been acquired for (approximately) 32 subjects, using a temporary alpha of 0.01 to mitigate inflation of Type I error probability due to multiple testing. Results of interim data analysis will be shared with Data Safety Monitoring Board, which will advise the principal investigator on whether to continue with the study.

Planned sample size of 64 will provide nearly 80% power, using the final alpha of 0.05, to detect a difference between groups on a numerical outcome variable for which the effect size is approximately 0.7, in the sense that a typical person in the treatment group would be approximately seven-tenths of one standard deviation better than a typical person in the control group. This is slightly greater than the effect size of approximately 0.6 observed by Mathai and colleagues for the exercise endpoint, but we anticipate being able to reduce variability by considering change scores from baseline to 3 months rather than just the final results at 3 months.

Each numerical outcome variable will be examined for approximate normality, and appropriate corrective action (e.g., log transformation prior to further data analysis) will be considered if approximate normality is untenable. A linear mixed model will be fit relating each outcome variable to group (between-subjects factor: treatment vs. placebo) and time (within-subjects factor: baseline vs. 3 months), with random effects for subjects and embedded linear contrasts to compare groups on change from baseline to 3 months. Although randomization is anticipated to balance groups on demographic and clinical characteristics, in the unlikely event that groups are imbalanced we can modify the linear mixed modeling to adjust for any covariates on which groups are imbalanced. Loss to follow-up is anticipated to be small, but in the unlikely event of more than 10% attrition from either group we can employ multiple imputation or another method for handling missing data. Groups will be compared on adverse events (e.g., re-hospitalization) using Fisher's exact test.

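### The two-visit random-subject model implies equal variance at baseline and 3 months; with truncated baseline hemodynamics and optional repeat catheterization, the standard errors for mean pulmonary pressure and vascular resistance can be wrong

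*Combined protocol and SAP*

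**What the plan says.** - **Model (Section 6).** Every outcome gets one mixed model with arm and visit as its two factors, fitted "with random effects for subjects and embedded linear contrasts to compare groups on change from baseline to 3 months". No residual covariance, visit-specific variance or robust standard error is named. Log transformation is offered where normality fails.
- **Entry (Section 4).** Patients must have "Pulmonary artery mean pressure >25 mm Hg, pulmonary capillary wedge pressure >15 mmHg, and pulmonary vascular resistance >3 WU" at a catheterization within 3 days of planned randomization. No other baseline catheterization is described, so the qualifying one also supplies the hemodynamic baseline.
- **Follow-up (Section 2).** At 3 months, "an echocardiogram, right heart catheterization, six minute walk, laboratory tests, and quality of life questionnaire will be repeated if clinically indicated".
- **Endpoints (Section 2, secondary outcomes).** Pulmonary pressures, vascular resistance and cardiac index are defined as percent change from baseline.
- **Missing data (Section 6).** Loss to follow-up is expected to be small. Multiple imputation or another method is an option, not a commitment, if attrition in either group passes 10%.

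**The concern.** With two visits, a subject random intercept plus a common residual is compound symmetry: one variance serves both visits. Mean pulmonary pressure and vascular resistance are bounded below at entry and free at 3 months, so their variances may well differ. A patient with a baseline value only still contributes to the shared variance. If baseline spread is the narrower, such patients pull the shared variance down. The contrast on change, which depends heavily on the scarcer 3-month values, then gets too small a standard error.

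At stake are the confidence intervals and p-values for these secondary outcomes. The error does not need selective missingness or a difference in missingness between the arms.

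**Working it through.** **1. The plan's own figure.** "Sample size was calculated at 32 patients per arm, 64 patients total", and "Planned sample size of 64 will provide nearly 80% power, using the final alpha of 0.05", for a "numerical outcome variable for which the effect size is approximately 0.7". With 32 per arm, 0.7/√(2/32) = 2.80, and Φ(2.80 − 1.96) = Φ(0.84) = 0.80. The noncentral t version (62 df) gives 78.7%. The stated power is reproduced (two-sided test assumed), and this point does not change it.

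**2. What truncation does to the variances.** Assume a normal outcome with source SD 1, entry cut-off c, and correlation ρ before truncation. With λ = φ(c)/(1 − Φ(c)):
- baseline variance v1 = 1 + cλ − λ²
- 3-month variance v2 = ρ²v1 + 1 − ρ²
- covariance v12 = ρv1

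At c = 0, λ = 0.798 and v1 = 0.363. Then v2 = 0.841 for ρ = 0.5 (ratio 2.3) and 0.688 for ρ = 0.7 (ratio 1.9). At c = 1, v1 = 0.199, and the ratios are 4.0 and 3.1.

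**3. Complete pairs.** For c = 0 and ρ = 0.5, the true variance of a change is 0.3634 + 0.8408 − 2(0.1817) = 0.8408. The equal-variance model settles on σ² = 0.6021 and correlation w = 0.3018, giving 2 × 0.6021 × (1 − 0.3018) = 0.841. The two agree, so unequal variance alone causes no error.

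**4. Half of the 3-month values missing at random, same c and ρ.** Let p = 0.5 be the share with a pair. The fitted σ² and w minimize

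p[ln σ²(1+w) + A/(σ²(1+w)) + ln σ²(1−w) + B/(σ²(1−w))] + (1−p)[ln σ² + v1/σ²],

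with A = (v1+v2+2v12)/2 = 0.7838 and B = (v1+v2−2v12)/2 = 0.4204. The solution is σ² = 0.5188, w = 0.2695. Per-arm variance of the estimated mean change, times the number randomized:
- Model: σ²(1−w²)/p + (1−w)²σ² = 0.962 + 0.277 = 1.239.
- True: (v2 + w²v1 − 2wv12)/p + (1−w)²v1 − 2(1−w)(v12 − wv1) = 1.539 + 0.194 − 0.122 = 1.610.

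The standard error ratio is √(1.239/1.610) = 0.877, about 12% too small. Large-sample Type I error is 2Φ(−1.96 × 0.877) = 8.6%.

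**5. Range.** The same formulas at c = 0 and 1, ρ = 0.5 and 0.7, beside simulated null trials (32 per arm, 3,000 per scenario, cut-off 0, 0.5 or 1 SD, missingness depending on baseline equally in both arms):

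| Missing at 3 months | SE ratio (formula) | Type I (formula) | Type I (simulated) |
|---|---|---|---|
| 10% | 0.97-0.98 | 5.4-5.8% | 5.2-6.2% |
| 30% | 0.90-0.95 | 6.3-7.8% | 6.3-8.6% |
| 50% | 0.82-0.91 | 7.6-10.9% | 7.2-11.2% |

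An unstructured covariance gave 4.2-5.8% throughout the simulation. Separate runs with purely random missingness gave 6.4-8.2% at 30% and 7.4-11.0% at 50% for the random-intercept model.

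**6. Where the error shrinks or reverses (simulated).**
- Right-skewed outcome on the raw scale, correlation 0.5: variance ratio 1.4-1.7, Type I error 5.3-6.2% at 30% missing and 5.9-6.3% at 60%.
- 3-month variance 0.5-0.7 of baseline in both arms: standard error about 4% too large at 30% missing and 5-13% too large at 60%; Type I error 3.1-4.9%.
- Outcome truncated only through its correlation with a truncated variable (cut-off 0.5 SD): 5.8% and 7.6% at 30% and 50% missing for correlation 0.8; 4.8% and 3.9% for correlation 0.
- Untruncated baseline, as for the walk: 4.5-5.4%.

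**The case against.** Four arguments have force.

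*The wording does not fix the covariance.* This is correct. A reader might infer that the plan forces equal variances. It does not, because visit-specific residual variances would fit the same sentence. Equal variance is the ordinary reading and a common software default, and nothing in Section 6 rules it out.

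*Multiple imputation would remove the problem.* Largely true if it is done. Simulated imputation from baseline and group (1,000 trials, correlation 0.5, cut-off 0 or 1 SD, 30-70% missing) gave 2.7-5.1% Type I error. But the clause is optional and speaks of attrition. A patient who attends at 3 months and is not catheterized has not obviously been lost, so the clause may never be triggered.

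*Percent change is one value per patient, so no two-visit variance is pooled.* True if the endpoint is analyzed as defined. Section 6 nevertheless applies the baseline-versus-3-months model to every outcome. The two sections need reconciling, and until then this defense cannot be relied on.

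*Not all hemodynamic outcomes are truncated.* Also correct. A reader might infer that all five (three pressures, resistance, cardiac index) are tested above 5%. Only mean pulmonary pressure and vascular resistance have thresholds of their own. Systolic and diastolic pressure are affected indirectly, and cardiac index has no entry threshold. Wedge pressure has one but is not a listed outcome.

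**Conclusion.** The point holds conditionally. If the model is fitted with a random intercept and one residual variance, and many patients lack a 3-month catheterization, the standard error of the contrast on change is misestimated for mean pulmonary pressure and vascular resistance, and to a lesser degree for systolic and diastolic pressure. A reader might infer that these standard errors are simply too small. The documents do not support that. The direction depends on which visit has the larger variance, and the size depends on truncation depth, correlation and missing share, none of which is given.

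Under the assumptions in the table, the inflation is slight at 10% missing, modest at 30%, and material at 50% or more. With complete pairs there is none. The primary outcome is essentially unaffected: with no entry threshold on walk distance, there is no built-in reason for unequal variances, even though its repeat falls under the same optional rule.

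This concerns error bars only. Selection bias from catheterizing only some patients at 3 months is a separate and larger matter.

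**What to change.** In Section 6, replace the subject random-effects wording with: fixed effects for group, time and group-by-time; an unstructured 2x2 covariance across the two visits, so that each visit has its own variance; and Kenward-Roger degrees of freedom. Keep the contrast on change.

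Reconcile the percent-change endpoints in Section 2 with this model. For example, analyze pressures, resistance and cardiac index on the log scale, so that the contrast is a log-ratio that can be reported as a percentage.

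State whether the missing-data clause covers catheterizations not performed, and whether imputation is then required.

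The covariance change costs one variance parameter and a sentence of text. In simulation the SD of the estimate differed by under 2%, and with complete pairs the walk result is the same. It protects in either direction of unequal variance. It does not recover missing catheterizations or remove selection in who receives them.

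### The primary contrast on change in walk distance is valid, but by default it does not adjust for baseline walk distance, so it may give up power at no saving

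*Combined protocol and SAP*

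**What the plan says.** Section 6 (Statistical design) fits a linear mixed model relating each outcome to "group (between-subjects factor: treatment vs. placebo) and time (within-subjects factor: baseline vs. 3 months", with subject random effects and "embedded linear contrasts to compare groups on change from baseline to 3 months". Baseline walk distance is therefore one of the two responses. It is not a covariate, and nothing says that the arms share a baseline mean.

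The power paragraph moves from an effect of about 0.6, seen in an earlier study, to about 0.7 because "we anticipate being able to reduce variability by considering change scores from baseline to 3 months". No correlation or SD is given. The sample size is 32 per arm, and "Planned sample size of 64 will provide nearly 80% power, using the final alpha of 0.05".

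Covariates appear once, as a contingency: "in the unlikely event that groups are imbalanced we can modify the linear mixed modeling to adjust for any covariates" on which they differ. Baseline walk distance is not named there.

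Section 2 (Trial design) already collects the covariate: "At baseline, a 6 minute walk test and quality of life questionnaire will be performed". The 3-month repeat is less certain, since there the "six minute walk, laboratory tests, and quality of life questionnaire will be repeated if clinically indicated".

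**The concern.** The plan chooses change scores in order to cut variability. With equal SDs at the two visits they do so only if the correlation r between baseline and 3-month walk distance exceeds 0.5; below that they add variability. Using the same baseline value as a covariate cuts variability, in large samples, at any non-zero r. The plan thus depends on a condition that it does not state and does not need.

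This matters because the trial is small, has one primary outcome and is planned at just under 80% power with no allowance for attrition. The imbalance clause does not close the gap. It is optional, it is triggered by the data, and a covariate added only as a main effect leaves the change contrast unchanged when pairs are complete.

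**Working it through.** **Inputs from the plan (section 6).** 32 per arm, 1:1 allocation, alpha 0.05, effect about 0.7 on change scores, effect about 0.6 from the earlier study.

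**Assumptions not in the documents.** Two-sided test; 0.6 is a final-value effect; ratio k of baseline SD to final SD between 0.8 and 1.2; normal data; complete pairs unless stated; baseline walk done before treatment starts.

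**1. The plan's own figure.** Noncentrality 0.7 × √(32/2) = 2.8 on 62 df gives power 78.7% (80.0% by the normal approximation). The stated power reproduces. An effect of 0.6 gives 65.6%.

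**2. What the contrast is.** In one simulated data set (r = 0.7), the planned mixed-model contrast and a plain comparison of change scores both gave 0.536 with SE 0.185. Adding another covariate as a main effect left both figures unchanged. ANCOVA on baseline gave SE 0.176.

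**3. Variances.** Set the final SD to 1 and the baseline SD to k.

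- Change score: 1 + k² − 2rk
- Baseline-adjusted: 1 − r²
- Difference: (1 + k² − 2rk) − (1 − r²) = (k − r)²

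The difference is never negative and is zero only when r = k. With k = 1, the adjusted variance is (1 + r)/2 of the change-score variance.

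**4. The r implied by going from 0.6 to 0.7.** Solve 0.6/√(1 + k² − 2rk) = 0.7. The variance of change must be (0.6/0.7)² = 0.735, so r = (1 + k² − 0.735)/(2k).

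**5. Power at that r.** Simulation with the slope estimated, 32 per arm, 100,000 runs per setting:

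| k | r | SD of change | Adjusted SD | Power, change | Power, ANCOVA | ANCOVA n per arm giving about 79% |
|---|---|---|---|---|---|---|
| 0.8 | 0.566 | 0.86 | 0.82 | 78.7% | 81.1% | 31 (79.8%) |
| 1.0 | 0.633 | 0.86 | 0.77 | 78.6% | 85.6% | 27 (78.9%) |
| 1.2 | 0.711 | 0.86 | 0.70 | 79.0% | 91.6% | 23 (79.7%) |

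Type I error was 0.050 for both methods at all three k (400,000 runs).

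**6. Other values of r** (k = 1, final-value effect 0.6; final values alone give 65.6%):

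| r | Change | ANCOVA |
|---|---|---|
| 0.4 | 58.1% | 72.7% |
| 0.5 | 65.7% | 77.3% |
| 0.7 | 86.2% | 90.7% |
| 0.8 | 96.2% | 97.4% |

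**7. Rounding of the two approximate effects** (k = 1). Taking 0.65 and 0.65 gives r = 0.50 and power 72.4% vs 83.3%. Taking 0.55 and 0.75 gives r = 0.73 and power 83.8% vs 88.0%.

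**8. Where nothing is gained.** At k = 0.8 and r = 0.7, (k − r)² is only 0.01 and power is 90.6% vs 90.7%. At k = r = 0.8 it is zero, and estimating the slope costs 0.2 points (97.6% vs 97.4%).

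**9. Fewer 3-month walks.** Complete-pair analyses, k = 1, r = 0.633, change vs ANCOVA: 29 pairs per arm, 74.6% vs 81.9%; 24 pairs, 66.2% vs 74.0%; 16 pairs, 48.3% vs 55.0%. Losing pairs can cost more power than adjustment restores.

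**The case against.** **Nothing is wrong as it stands.** The contrast is valid, prespecified and delivers the power claimed. That is right, and the point is put as efficiency only.

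**The size is assumed.** No r or SD is given, nothing says that 0.6 was a final-value effect, and the study behind it is not in the reference list. The top of the range needs a baseline SD 20% above the final SD, which nothing in the documents supports. Holding 0.7 on the change scale with equal SDs gives smaller gains in simulation (20,000 runs): 79.4% vs 84.6% at r = 0.7, 79.1% vs 82.5% at 0.8, and 79.0% vs 80.2% at 0.9. This stands as a limit on the size, not on the direction.

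**Low correlation contradicts the plan's premise.** With equal SDs the plan expects r above 0.5, so the figures at r = 0.4 are a stress test, not an expected benefit. That is fair. They show what adjustment protects against.

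**A mixed model keeps patients with only a baseline walk.** Step 9 drops them from both analyses. Against a likelihood mixed model that keeps them (32 randomised per arm, k = 1, r = 0.633, 40,000 runs), complete-pair ANCOVA still leads: 74.7% vs 81.9% at 29 pairs per arm, 67.2% vs 73.6% at 24, and 50.5% vs 54.8% at 16. The gain shrinks from about 7 to about 4 points but stays positive. At r = 0.8 with 0.7 on the change scale and 16 pairs, it is about 2 points.

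**The baseline walk may be late.** Section 2 allows it up to 3 days after the qualifying catheterization, and section 4 puts that catheterization within 3 days of planned randomization, so a walk after randomization is possible. A walk done after treatment starts would disturb the planned contrast as well, but the condition should be written down.

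**Conclusion.** The concern holds as a loss of efficiency. The planned contrast is unbiased, keeps its 5% type I error and has the power stated. By default it leaves out a covariate that the trial already collects.

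Under the plan's own move from 0.6 to 0.7, read as final-value to change score, adjustment is worth about 2 to 13 power points over SD ratios 0.8 to 1.2, and about 7 with equal SDs. It can be close to zero when r is near k, or when r is high with equal SDs. Confidence is high about the direction. The size rests on an unstated correlation and unstated SDs. The change is worth making because the largest loss found, 0.2 points, is small beside the likely gain.

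**What to change.** State in section 6: *The primary analysis of 6-minute walk distance will be an ANCOVA of the 3-month value on treatment group and baseline walk distance, fitted whether or not the groups are balanced.* Say also how patients without a 3-month walk are handled, so that the analysis stays consistent with the intent-to-treat commitment.

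Alternatively, keep the mixed model but give both arms a common baseline mean, with unstructured covariance for the two visits. This is valid only if baseline walks precede treatment, so that condition should be stated with it.

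The planned change contrast can remain as a sensitivity analysis. As an optional clarification, give the correlation assumed in going from 0.6 to 0.7 and say whether 0.6 was a final-value effect.

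The cost is a sentence or two and one model degree of freedom. Patients, visits, measurements, endpoint and sample size are unchanged. The choice should be fixed before outcome data are seen.

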The vasoreactive component of PH develops with long-standing PH. It is characterized by vasospasm, vasoconstriction, and eventually morphologic changes of the pulmonary vasculature. The degree of PH is considered "out of proportion" to the PCWP. In other words, PH persists independently of the PCWP. Pulmonary vascular resistance and the transpulmonary gradient are elevated. Diuretics are, therefore, ineffective for treatment of reactive PH, and other medical treatment options are limited. In HF, reactive PH is associated with worst outcomes. In one study involving HF patients, the presence of reactive PH carried a higher risk of death (HR: 1.55; 95% CL: 1.11, 2.20; $p < 0.001$)⁴.

Finally, no treatment option currently exists for reactive PH in the setting of HF. Multiple studies indicate that phosphodiesterase-5 inhibitors may be an effective therapy in this setting⁵⁻⁸. In particular, when patients with biventricular HF, poor right ventricular function, and increased transpulmonary gradient received sildenafil 20 mg three times a day, in addition to other HF medications, it resulted in a significant decrease of pulmonary pressures, improvement in right ventricular function, decrease in NTproBNP serum levels, as well a substantial improvement of the 6-minute walk distance by 91 ± 54 m.⁹ Importantly, there was a very modest reduction in pulmonary capillary wedge pressure, indicating that the reactive, and not the passive component of PH is the principal therapeutic target for sildenafil.

Clinical studies of sildenafil in HF are summarized in Table 1. The best results were obtained when the patients were selected based on the presence of reactive pulmonary hypertension, namely increased pulmonary vascular resistance and transpulmonary gradient.

No randomized controlled clinical trials, testing sildenafil in HF, selected patients based on these criteria. None of the trials, therefore, utilized the full potential of phosphodiesterase -5 inhibitors in HF. Specifically, the recent multicenter, double-blind, placebo-controlled, parallel-group, randomized RELAX trial included patients with unknown pulmonary pressures – they were not among inclusion criteria. Understandably, the trial failed to demonstrate favorable effects of sildenafil¹⁰.

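### Missing 3-month walks are handled only under missing at random, with an optional step above 10% attrition, so death or inability to walk never counts as a bad outcome in the primary result

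*Combined protocol and SAP*

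**What the plan says.** Section 3 (Objectives) sets the primary question as whether sildenafil "can improve exercise tolerance measured by 6 minute walk distance". Section 6 (Statistical design in detail) states "Data will be analyzed on an intent-to-treat basis, as described below". It specifies a linear mixed model with group, time (baseline and 3 months) and random subject effects, and a contrast on the change between the two times. It expects little loss to follow-up and gives no rate. Its one explicit provision is that "in the unlikely event of more than 10% attrition from either group we can employ multiple imputation or another method for handling missing data". Adverse events are compared separately by Fisher's exact test.

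Three other places bear on the point:

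- The Scientific Rationale says that in heart failure "the presence of reactive PH carried a higher risk of death" (hazard ratio 1.55).
- Section 2 (Trial design) makes the repeat of the 3-month tests, including the walk, depend on clinical indication. It also has the coordinator capture clinical events such as unscheduled hospital visits.
- Section 4 (Eligibility) excludes patients with a previous transplant or assist device, and those likely to have a transplant or other major surgery during the study.

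No section says how a patient who dies, or cannot walk at 3 months, enters the walk analysis. There is no assigned value, rank, composite or sensitivity analysis.

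**The concern.** Bias from missing walks depends on the reasons for loss and on how they differ between arms. A percentage does not capture either. Three losses in an arm of 32 is 9.4% and stays under the trigger; four is 12.5% and passes it. Three patients too ill to walk in one arm and none in the other would prompt no extra step.

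The mixed model keeps patients who have only a baseline walk, but under missing at random it treats them like similar patients who did walk. That assumption is hard to defend for death or worsening heart failure. Multiple imputation in its usual form makes the same assumption. Intention to treat does not settle the matter, because it supplies no value for a walk that could not take place.

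An arm that loses its sickest patients therefore looks better than it is. Loss from placebo hides benefit, and loss from sildenafil can create an appearance of it. The clinical-indication condition in section 2 adds a second route, since whether a walk is done may then depend on the patient's state.

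**Working it through.** **Inputs from section 6.** "Sample size was calculated at 32 patients per arm, 64 patients total"; allocation 1:1; final alpha 0.05 (taken as two-sided); effect size 0.7 SD.

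**The plan's own figure.** The plan says "Planned sample size of 64 will provide nearly 80% power, using the final alpha of 0.05". With 32 per arm and 0.7 SD, the normal approximation gives 79.96% and the exact two-sample t-test 78.7%. The figure reproduces as two-sided with no allowance for dropout. A one-sided test would give 87.6%.

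**Assumptions.** The documents give no walk SD, death rate or dropout rate. I take normally distributed changes with SD 1 and three losses from one arm only.

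**Size of the shift.** If the three lost patients lie on average m SD below their own arm's mean, the mean of the 29 who remain rises by 3m/29. For patients drawn from the lowest fraction p of a normal distribution, m = φ(z_p)/p.

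- Lower half, p = 1/2: m = 0.3989/0.5 = 0.798; shift 3 × 0.798/29 = 0.083.
- Worst third, p = 1/3: m = 0.3636/0.3333 = 1.091; shift 3 × 1.091/29 = 0.113.
- Three worst, p = 3/32: m = 0.1674/0.09375 = 1.785; shift 3 × 1.785/29 = 0.185. In samples of 32 the simulated value is 0.18.

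**Effect on the test.** Simulated two-sided t-test on change, 32 per arm before loss:

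| Three lost from one arm | Shift (SD) | Share of 0.7 | Estimate when truth is 0.7, placebo loss | Power | Rejection under no effect, sildenafil loss |
|---|---|---|---|---|---|
| At random from lower half | 0.08 | 11% | 0.62 | 66–67% | 5–6% |
| At random from worst third | 0.11 | 16% | 0.59 | 63% | 7% |
| The three worst changes | 0.18 | 26% | 0.52 | 56–57% | 12% |

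Losing three patients from one arm with no selection leaves 76.6% power (29 against 32). Of the fall from 78.7%, about 2 points are therefore due to the smaller sample and the rest to selection.

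**Does the planned mixed model remove the shift?** I assume a correlation of 0.7 between baseline and 3 months, no treatment effect, and the three worst sildenafil changes missing. The mixed model then gives +0.15 SD with about 13.5% rejection (200 runs, Monte Carlo error about 2.4 points). The complete-case analysis gives +0.17 SD and 12.2% (5,000 runs). The model reduces the shift only slightly.

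**When it does not matter.** With losses split 2:1 between the arms, from the worst third or lower half, the shift is 0.02 to 0.04 SD and rejection stays at about 5%. With three similar losses in each arm the estimate is unbiased. If those losses are unselected, power with 29 per arm is 74.5%.

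**The case against.** The best defence is that the plan already has a likelihood-based analysis at every attrition rate. A reader might infer that patients without a 3-month walk are dropped, or that nothing is done for them below 10%. The text does not support that: the mixed model retains anyone with a baseline walk. A reader might also infer that imputation is the rule above 10%. The wording is optional and permits an unnamed alternative. Both corrections stand. What remains is that missing at random is the wrong assumption for death or inability to walk, and that a method chosen after the data are seen is not pre-specified.

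The defence can add that follow-up is only 3 months, that likely transplant and major-surgery candidates are excluded, that the hazard ratio of 1.55 is relative and gives no 3-month death rate, and that clinical events are captured and adverse events compared by arm. These points reduce the expected number of affected walks. They do not cover death or worsening heart failure, and the separate Fisher's test is not connected to the walk result.

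Finally, a simulation that removes the worst changes and then ranks those patients lowest will show worst-rank analysis recovering nearly all the power. That is close to circular and is no evidence for the method. The case for it is that it counts death and inability to walk as bad outcomes.

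**Conclusion.** The gap is real and worth correcting. The plan has no rule for death or inability to walk in its primary analysis, and its trigger looks at a percentage when the reason and the arm are what matter.

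Three illness-related losses confined to one arm would move the contrast by about 0.08 to 0.11 SD in the milder scenarios. The upper bound is 0.18 SD, about a quarter of the design effect. This rests on normal changes, one-sided loss and exactly three patients, none of which the documents establish.

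A reader might take 12% as the trial's false-positive rate or 56% as its power. Neither follows. Both hold only if the three worst changes all vanish from a single arm, and comparable losses in both arms largely cancel. The direction of bias cannot be predicted from the documents.

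**What to change.** In section 6:

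- Remove the 10% trigger. Keep the mixed model as primary and state that its likelihood-based handling of missing walks applies at any rate.
- Record the reason for every missing 3-month walk.
- Pre-specify a supportive rank-based comparison of walk change. Patients who died, or could not walk because of heart failure or cardiac replacement, rank below all observed changes.
- Report deaths and inability to walk by arm beside the primary result.

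In section 2, state that the 3-month walk is done for all participants able to attempt it.

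The cost is some wording, one data field and one additional analysis whose result is not in metres. The primary model and its estimate in metres are unchanged.
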